5.3. MODIFIED INTENT-TO-TREAT [mITT]

The mITT analysis populations include all enrolled mutation positive subjects who receive any treatment post-baseline and have at least one assessment for the analysis primary parameter (PiB-PET SUVR for final analysis, CDR Global for both the interim analysis and the final analysis) prior to the associated treatment period (as a baseline assessment) and a post-baseline assessment. For analysis of clinical/cognitive endpoints or non-PET biomarker endpoints, the mITT population identified based on CDR Global should be used.

Author: [REDACTED]

Version Number:

7

Version Date:

07Dec2023

[figure not shown]
Template No.: CS_TP_BS016 Revision 6

Reference: CS_WI_BS005

Effective Date: 02Dec2019

There will be three separate mITT populations:

1. OLE Gant mITT: Any subjects in the OLE meeting mITT criteria using OLE baseline (defined as the last assessment time for the analysis primary parameter prior to the first dose of OLE treatment) as the baseline reference point. Refer to figure below where the data contributing to the population is highlighted in yellow (and denoted with '(Tx)') for the OLE period, regardless of double-blind treatment, with controls (further described in [Section 5.4](#)) highlighted in green from both placebo double-blind only subjects and matched controls from DIAN-OBS.

2. OLE Gant All Gant exposure mITT: Any subjects treated with gantenerumab in both the DB and OLE who meet mITT criteria using DB baseline as the baseline reference point. Refer to figure below where the data contributing to the population is highlighted in yellow (and denoted with '(Tx)') for subjects treated with gantenerumab in both DB and

Author: [REDACTED]

Version Number:

7

Version Date:

[figure not shown]
07Dec2023

Template No.: CS_TP_BS016 Revision 6

Reference: CS_WI_BS005

Effective Date: 02Dec2019

OLE, with main set controls (further described in [Section 5.4](#)) highlighted in green from both placebo double-blind only subjects and matched controls from DIAN-OBS, and an additional set of extended controls (using DB and OLE baseline values for double-blind placebo subjects entering OLE) in a different shade of green to be added to the main set controls to form a second set of controls for the population.

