5.4.2. INTERNAL SET CONTROLS

The internal set controls are defined as the placebo data from the double-blind period among subjects who did not enter the open-label extension.

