5.4.4. EXTENDED SET CONTROLS

The extended set controls are defined as the main set controls plus the double-blind baseline and OLE baseline values for subjects treated with placebo during the double-blind period who entered the OLE. This set will be an additional set used with the OLE Gant All Gant exposure mITT to add further long-term follow-up given that the two timepoints will differ by over four years for subjects added to this control group.

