16.2.3. PRIMARY ANALYSIS OF KEY SECONDARY EFFICACY VARIABLES

16.2.3.1. Primary Analysis of CDR-SB

The primary analysis will be on the All Gant Exposure mITT, with other baseline covariates (such as baseline EYO) defined in the same way as baseline for the associated population. The recurrent progression is defined as any progression which is either the first increase in CDR-SB above baseline or any progression above the highest preceding post-baseline value identified as a progression, where progression above the preceding value must be observed at two consecutive measurements unless the progression occurs at the last measurement. Subjects without a progression event at their last measurement will be censored at the time of that measurement. The time-to-event is the time elapse between the two visits where the recurrent progression is observed, or the time since the baseline assessment for the first progression. Subjects can contribute multiple records to the analysis (i.e., once for each progression and potentially for censoring at the time of last measurement). The same definition will be applied to all controls as defined in [Section 5.4](#). The Cox proportional hazards model employing the Andersen-Gill method (Prentice RL, 1981) with robust variance estimator will be used to compare the hazards of recurrent progression in CDR-SB between population and all controls. The model will include treatment group and baseline EYO as the fixed effects. Should the model produce a two-sided p-value less than 0.10, a sensitivity analysis will be conducted using the shared frailty method (add reference).

Author: [REDACTED]

Version Number:

7

Version Date:

07Dec2023

Template No.: CS_TP_BS016 Revision 6

Reference: CS_WI_BS005

Effective Date: 02Dec2019

Analyses will be conducted separately for baseline asymptomatic and symptomatic subjects.

The same analysis will be applied to the OLE Gant mITT population and the OLE Gant All Gant exposure mITT populations, along with all controls. The analysis will also be conducted for each of the three mITT populations based on the baseline asymptomatic and symptomatic subjects presented separately. A Kaplan-Meier figure will be generated for baseline asymptomatic subjects for all three mITT populations and associated controls.

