16.2.3.2. Primary Analysis of CDR Global

The primary analysis will be on the All Gant Exposure mITT, with all the other baseline covariates (such as baseline EYO) defined in the same way as baseline for the associated population. The time to the first disease progression is defined as the time from the baseline to the first visit where CDR Global is greater than CDR Global baseline value, where a progression is considered an increase above baseline observed at two consecutive measurements unless the progression occurs at the last measurement. Subject without progression will be censored at their last measurement.

The Cox proportional hazards model will be applied to compare the hazards of disease progression in CDR Global between each of the three mITT population separately and all

Author: [REDACTED]

Version Number:

7

Version Date:

07Dec2023

Template No.: CS_TP_BS016 Revision 6

Reference: CS_WI_BS005

Effective Date: 02Dec2019

controls. The models will include the treatment group (specifically gantenerumab and controls) and baseline EYO as the fixed effects.

Analyses will be conducted separately for baseline asymptomatic and symptomatic subjects. A Kaplan-Meier figure will be generated for baseline asymptomatic subjects for all three mITT populations and associated controls.

Spaghetti plot of EYO for each participant will be presented for each of the three mITT populations. Lines and data points will be coded by different color/symbol for different CDR groups (without progression, with progression) and doses. This figure will be generated by Washington University team.

16.2.3.3. Primary Analysis of OLE Cognitive Composite, FAS, MMSE, Tau-PET SUV, CSF NfL and CSF MTBR243

The annual disease progression between the OLE Gant mITT population and all controls (with the exception of internal controls only for Tau-PET SUV) will be compared using a linear mixed effects (LME) model. CSF NfL will be log transformed for the analysis. The LME model will include time since baseline (in years: treated as continuous), treatment group (the OLE Gant mITT and all control), interaction between the treatment group and time, and random intercepts and slopes for each subject as the random effects. The unstructured covariance will be used to model the covariance between random intercepts and random slopes and will be modelled separately for baseline asymptomatic and symptomatic subjects.

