16.2.4.1.6. Longitudinal Logistic Regression Model

For subjects in the All Gant exposure mITT, at each post-baseline visit including all the OLE visits, the CDR-SB value will be compared to that of the previous visit (rather than compared to highest value of previous visits), if the value of the later visit is larger than the previous one, the disease progression status is defined as 1; otherwise, the disease progression status is defined as 0. The same definition will be applied to all controls. Longitudinal logistic regression model will be applied to compare the odds of disease progression in CDR-SB between the All Gant exposure mITT and all controls. The model will include treatment group, time since baseline (continuous), interaction between the treatment group and time, and baseline EYO as the fixed

Author: [REDACTED]

Version Number:

7

Version Date:

07Dec2023

Template No.: CS_TP_BS016 Revision 6

Reference: CS_WI_BS005

Effective Date: 02Dec2019

effects, and a subject-level random intercept will also be included to account for the within-subjects correlation among the disease progression status.

Baseline CDR status will also be included in the model along with the three-way interaction between time, treatment group, and CDR status to determine if treatment before symptom onset is different from after symptom onset.

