16.4. EVALUATION OF THE ASSOCIATION BETWEEN AMYLOID REDUCTION AND CLINICAL/COGNITIVE CHANGES

To evaluate if amyloid reduction is associated with clinical/cognitive benefits, the following analysis will be conducted.

1. The correlation between the change in PiB-PET SUVR and the change in clinical/cognitive

Author: [REDACTED]

Version Number:

7

Version Date:

07Dec2023

Template No.: CS TP BS016 Revision 6

Reference: CS WI BS005

Effective Date: 02Dec2019

endpoints of CDR SB and OLE Cognitive Composite will be evaluated using Spearman correlation. This correlation will be evaluated using the annual rate of change and the change from baseline to the end of OLE, respectively. The correlation will also be estimated for the subjects on double-blind gantenerumab treated group vs combined double-blind placebo and double-blind solanezumab treated group, or for subgroups defined below in item #2 (Amyloid normal group, Amyloid abnormal to normal group, and the rest). This analysis will be applied to the Gant OLE mITT and All Gant exposure mITT, respectively. Additionally, all controls will also be included to evaluate the correlation without any treatment.

2. Each subject will be categorized into 3 groups as defined in the first paragraph in [Section 16.2.4.1.1](#). The LME model will be applied to the All Gant exposure mITT population and all controls to compare the annual rate of change among the 3 subgroups for key secondary efficacy variables.

Baseline PiB PET SUVR and baseline EYO will be included as covariates in these analyses when evaluating the correlation of the annual rate of change.

For all these analyses, figures of model estimated mean over time by treatment arms or spaghetti plots of individual data over time/EYO by treatment arms will be presented as deemed necessary by Washington University team and may be included in CSR as needed.

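### The slope model in SAP 16.2.3.3 compares gantenerumab with non-randomised controls without an EYO term, so disease stage can mix with treatment; neither the size nor the direction of the bias is known

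*SAP*

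**What the plan says.** SAP 16.2.3.3 sets out its linear mixed effects model (LME) in full. The fixed part is given as "The LME model will include time since baseline (in years: treated as continuous), treatment group (the OLE Gant mITT and all control", with the group-by-time interaction. Random intercepts and slopes are added, and asymptomatic and symptomatic participants are handled separately. SAP 7.1 lists EYO among the covariates but leaves inclusion to each analysis section, so it does not supply the missing term.

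Elsewhere the SAP does adjust for EYO:
- CDR-SB, recurrent-event Cox (16.2.3.1): "The model will include treatment group and baseline EYO as the fixed effects".
- CDR Global, first-progression Cox (16.2.3.2): "The models will include the treatment group (specifically gantenerumab and controls) and baseline EYO as the fixed effects".
- Longitudinal logistic model (16.2.4.1.6): "interaction between the treatment group and time, and baseline EYO as the fixed" effects.
- Correlation of annual rates of change (16.4): "Baseline PiB PET SUVR and baseline EYO will be included as covariates in these analyses".

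The comparison is not randomised. Internal controls are "the placebo data from the double-blind period among subjects who did not enter the open-label extension" (5.4.2). External controls come from DIAN-OBS and start at their first eligible visit (5.4.1, 6.2.2). The first treated population is "Any subjects in the OLE meeting mITT criteria using OLE baseline" as time zero (5.3). For placebo participants who went on to the OLE, 5.4.4 says of double-blind and OLE baseline that "the two timepoints will differ by over four years for subjects added to this control group".

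**The concern.** The quantity tested is a difference in annual rate of change. If that rate depends on disease stage, and treated participants sit at a different stage from controls, the difference contains stage as well as treatment. The design makes such a gap likely in the OLE Gant mITT, because its clock starts years after the point at which internal controls start. Fitting by CDR status re-sorts participants and removes only part of the gap. The SAP adjusts for EYO when it correlates annual rates of change in 16.4 but not when it compares them in 16.2.3.3, and gives no reason.

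At stake is the reading of these slope contrasts, and of the analyses that borrow the model: the CDR-SB LME in 16.2.4.1.3, the remaining secondary variables in 16.2.5, and the LME rows of Table B. A difference, or the absence of one, could be taken for a drug effect when it partly reflects stage.

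**Working it through.** The plan states no figure for this comparison, so there is none to reproduce. Sizes below are illustrations.

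**1. Count.** SAP 16.2.1.1 lists nine key secondary variables. Two use Cox models (CDR-SB, CDR Global), two use MMRMs without controls (CSF pTau181, CSF Amyloid Beta1-42/40), and the other five use this LME. MTBR243 is in the section title but not in that list.

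**2. Bias if the rate changes linearly with EYO.** Let g be the change in rate per EYO year and D the treated-minus-control EYO gap within a CDR stratum. Assume g = 0.01 to 0.03 SD/yr per year, D = 2 or 3 years, two years of treated follow-up (the interim focus, SAP 17) and four years of control follow-up.
- Slope fixed by baseline EYO: bias = g x D. At D = 2 this is 0.02 to 0.06 SD/yr; at D = 3, 0.03 to 0.09.
- Rate steepening within person: the mean treated rate sits 1 year into follow-up and the control rate 2 years in, so bias = g x (D - 1). At D = 2 this is 0.01 to 0.03; at D = 3, 0.02 to 0.06.

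Both run against gantenerumab for these D. The second reverses if D is below 1 year.

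**3. Against the standard error.** Assume 35 treated per stratum (60 to 90 OLE entrants, Protocol Appendix 3, 4.1.2, split evenly gives 30 to 45), 60 controls, slope SD 0.15, residual SD 0.3 and EYO SD 4. With g = 0.03 and annual visits, the variance of a participant's slope is:
- treated: 0.0225 + 0.0144 + 0.09/2 = 0.0819
- control: 0.0225 + 0.0144 + 0.09/10 = 0.0459

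SE = sqrt(0.0819/35 + 0.0459/60) = 0.056. A bias of 0.06 or 0.09 then gives two-sided rejection of about 19% or 36% with no treatment effect. Simulation of the LME gave 19.4% and 35.1%. Across the linear cells, simulated rejection was 7% to 35% (fixed slope) and 5% to 19% (steepening). With g = 0 it was 4.5%.

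**4. Sigmoid course.** SAP 16.2.4.1.5 models progression as a logistic curve in EYO. Take f(x) = 3/(1 + exp(-(x - 2)/3)), with assumed height, scale and midpoint. Mean two-year decline:
- Asymptomatic, control from -6: (0.358 - 0.195)/2 = 0.081. Treated from -4: (0.626 - 0.358)/2 = 0.134. Difference 0.053 against gantenerumab.
- Symptomatic, control from +2: (1.982 - 1.500)/2 = 0.241. Treated from +4: (2.374 - 1.982)/2 = 0.196. Difference 0.045 toward gantenerumab.

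Past the midpoint the curve flattens, so later-stage participants decline more slowly.

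**5. Averaged over a population.** Assumed: entry EYO uniform from -15 to +10, error in estimated onset SD 2 to 6 years, entry only if under 5 years past true onset, treated shifted 4 or 5 years, no attrition, treated visits at years 0, 1 and 2. Expected slope differences, SD/yr:

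| | Asymptomatic | Symptomatic |
|---|---|---|
| Remaining EYO gap, years | 2.0 to 3.1 | 2.0 to 3.1 |
| No EYO, 4-year controls | 0.004 to 0.018 against | 0.027 to 0.041 toward |
| No EYO, 2-year controls | 0.018 to 0.034 against | 0.048 to 0.063 toward |
| EYO x time, 4-year controls | 0.016 to 0.024 toward | 0.002 to 0.028 toward |
| EYO x time, 2-year controls | 0.000 to 0.006 toward | 0.025 to 0.050 toward |

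Other variants of these inputs widen the unadjusted ranges to about 0.00 to 0.04 against and 0.02 to 0.06 toward, and the last symptomatic cell to about 0.01 to 0.05. Adding a quadratic in baseline EYO moved that cell only to 0.023 to 0.049: no EYO term removes the error in EYO as a marker of true stage.

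**The case against.** **Existing supplements.** The SAP already has models with EYO as the time axis for CDR-SB (16.2.4.1.4, 16.2.4.1.5) and the OLE Cognitive Composite (16.2.4.3). This stands and narrows the gap to FAS, MMSE, Tau-PET, CSF NfL and MTBR243. MMSE is also a component of the composite.

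**Other safeguards.** External controls are chosen on trial entry criteria, participants are split by CDR status, and plots over EYO are allowed. None adjusts the slope contrast, and the plots are optional.

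**The remedy is partial.** This stands. It works well for asymptomatic participants and only partly for symptomatic ones. The smaller symptomatic residual with 4-year controls comes from two errors offsetting, which is no reason to rely on it.

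**The illustration is generic.** This also stands. MMSE is collected about every six months in the OLE, double-blind PET at about years 1, 2 and 4, and double-blind tau PET came through an addendum. One annual schedule does not fit every endpoint.

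**Low stakes.** The endpoints are secondary and without multiplicity control (7.4), and the OLE ended early without a path to approval (SAP version history). This lowers the priority but does not make an unadjusted contrast interpretable.

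**Stronger readings.** A reader might infer that the omission works against gantenerumab, so that a null result hides a benefit. That needs a course that keeps steepening; the SAP's sigmoid can reverse the sign in symptomatic participants. A reader might also infer that the two-slope spline in 16.2.3.3 tests the post-OLE slope against the single control slope, which would be more exposed to stage. The text does not state that contrast.

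**Conclusion.** The omission is real: 16.2.3.3 has no EYO term, and no general section supplies one. Because the comparison is non-randomised and the time origins differ by design, the OLE Gant mITT slope contrast can mix stage with treatment. The exposure should be smaller where double-blind baseline is the treated time zero, as in the OLE Gant All Gant exposure mITT.

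The size is unknown. Gradient, gap, variances and control numbers above are all assumed, and the bias vanishes if stage has no effect on rate. Protocol Appendix 3, 1.4 reports no cognitive decline in the asymptomatic placebo group, so the gradient may be near zero for cognition there. The direction is not established either: the documents support neither a claim of masked benefit nor one of false efficacy.

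Not affected are the PiB-PET primary analysis, the Cox primary analyses of CDR-SB and CDR Global (also the interim primaries), and the MMRMs without controls. This is a cheap improvement to secondary analyses, not a flaw in the main conclusions.

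**What to change.** Keep the pre-specified LME. Add a sensitivity LME, first for FAS, MMSE, Tau-PET, CSF NfL and MTBR243, as follows:
- Include baseline EYO and baseline EYO x time, taken at each population's own baseline and at the analysis baseline for controls. A main effect alone shifts the intercept and leaves the slope contrast unadjusted.
- Fit by CDR stratum, with control follow-up cut at the treated follow-up length. Otherwise longer control follow-up can tilt the adjusted contrast toward gantenerumab where decline is steepening.
- In symptomatic participants allow a non-linear EYO term, and state that adjustment there is still only partial.
- Label the model as added after the interim.
- Report mean baseline EYO by group within CDR stratum, by splitting the table already planned in SAP 10.
- Do not read a slope difference as a treatment effect where the two models disagree.

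The cost is a few degrees of freedom and one extra run per endpoint; EYO is already derived for treated and control participants. The main drawback is that an analysis added after the interim carries less weight than a pre-specified one.

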16.2.3.4. Primary Analysis of CSF pTau181

To evaluate whether gantenerumab will continue to reduce the CSF pTau181 from OLE baseline, MMRM (without controls) will be used to test if the change from the OLE baseline to the end of OLE in CSF pTau181 is significantly less than 0 for the OLE Gant mITT population. The MMRM will include the OLE baseline CSF pTau181 and visit (treated as categorical) as the fixed effects. An unstructured variance-covariance matrix will be used to model the within-subject errors among the repeated measures. If the unstructured covariance structure matrix results in a lack of convergence, the following covariance structures will be assumed in sequence: heterogeneous Toeplitz, heterogeneous autoregressive, heterogeneous compound symmetry, and compound symmetry. The corresponding p-value and the 95% confidence interval for the estimated least squares mean change at each visit will be presented. If the upper bound of the 95% CI at the year 3 OLE visit is less than 0, it is concluded gantenerumab significantly remove amyloid plaque at year 3.

[REDACTED] [REDACTED]

Author: [REDACTED]

Version Number:

7

Version Date:

07Dec2023

Template No.: CS_TP_BS016 Revision 6

Reference: CS_WI_BS005

Effective Date: 02Dec2019

Figures of model estimated mean over time by treatment arms or spaghetti plots of individual data over time/EYO by treatment arms will be presented as deemed necessary by Washington University team and may be included in CSR as needed. The plots will also be presented separately for baseline asymptomatic and symptomatic subjects at the OLE baseline.

16.2.3.5. Primary Analysis of CSF Amyloid Beta1-42/40

To evaluate if treatment with gantenerumab increases CSF Amyloid Beta1-42/40, the MMRM as described in [Section 16.2.3.4](#) will be applied for the OLE Gant mITT and the MMRM as described in [Section 16.1.4.3](#) will be applied for the All Gant exposure mITT, with both asymptomatic and symptomatic subjects included within the same model.

16.2.4. SUPPLEMENTAL ANALYSIS OF KEY SECONDARY EFFICACY VARIABLES

16.2.4.1. Supplemental Analysis of CDR-SB

16.2.4.1.1. Subgroup Analysis for CDR SB

Each subject in the All Gant exposure mITT population and all controls will be categorized into 3 groups by comparing the baseline and the last available PiB SUVR values to 1.25: (1) Amyloid normal group (both the baseline and the last available PiB SUVR values <1.25); (2) Amyloid abnormal to normal group (the baseline PiB SUVR value ≥ 1.25 and the last available PiB SUVR value <1.25); (3) The rest (not in groups (1) and (2)). The model described in [Section 16.2.3.1](#) will be applied to the All Gant exposure mITT population and all controls to compare the hazard of progression in CDR SB among these 6 subgroups (i.e., 3 groups above assessed within baseline asymptomatic/symptomatic status).

A separate analysis will identify DIAN-TU-001 subjects as either PiB-PET SUVR normal or abnormal based upon the last post-baseline measurement for the subject. The model described in

Author: [REDACTED]

Version Number:

7

Version Date:

07Dec2023

Template No.: CS_TP_BS016 Revision 6

Reference: CS_WI_BS005

Effective Date: 02Dec2019

Section 16.2.3.1 will be applied to the asymptomatic subjects in the All Gant exposure mITT population where treatment groups are replaced with the three groups of PiB-PET SUVR normal, PiB-PET SUVR abnormal, and external controls, with the normal and abnormal groups being compared to the external controls and to each other. The model will also be run with factors of the number of post-baseline PiB-PET normal values (as a continuous measure to replace the normal/abnormal status) and the interaction of that variable with the treatment groups.

The model described in **Section 16.2.3.1** will be applied to the asymptomatic subjects in the All Gant exposure mITT population where treatment groups are replaced with the three groups of gantenerumab exposure, concurrent controls, and non-concurrent controls, with the gantenerumab exposure being compared to both sets of controls.

Figures of model estimated mean over time by treatment arms or spaghetti plots of individual data over time/EYO by treatment arms will be presented as deemed necessary by Washington University team and may be included in CSR as needed. The plots will also be presented separately for baseline asymptomatic and symptomatic subjects at the OLE baseline.

16.2.4.1.2. Cox Proportional Hazards Model for Time to First Disease Progression in CDR SB

The analysis models in **Section 16.2.3.2** (Cox proportional hazards model) will be applied to CDR SB. The same analysis will be repeated for the OLE Gant mITT population with 4 treatment groups (subjects on gantenerumab in the double-blind period, subjects on solanezumab in the double-blind period, subjects on placebo in the double-blind period, and all control) and will be repeated for the six subgroups defined in the first paragraph in **Section 16.2.4.1.1**. The same analysis may also be conducted for subgroups defined in the second paragraph in **Section 16.2.4.1.1**.

[REDACTED] [REDACTED]

Author: [REDACTED]

Version Number:

7

Version Date:

07Dec2023

Template No.: CS_TP_BS016 Revision 6

Reference: CS_WI_BS005

Effective Date: 02Dec2019

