Unique Identifier for this Version	Date of the Document Version	Author	Significant Changes from Previous Authorized Version
			primary interim parameters based on last post-baseline PiB-PET and based on concurrent / non-concurrent controls; changed MAC-Q and Tau PET to use internal controls only due to limited data for external controls; added figures to interim analysis; reference made to the Addendum of the Statistical Analysis Plan
■■■	■■■	■■■	Updated the model used for MTBR243 in Section 17, Table B from MMRM to LME; added MTBR243 to Section 16.2.3.3.
■■■	■■■	■■■	
 1. Add a mITT population definition based on CDR Global for the final analysis in section 5.3. Rationale for this change: Due to the unexpected pandemic, many participants were unable to travel to the study site for the PET scan, resulting in significant missing data, either at baseline or post-baseline. Therefore, a mITT population defined based on amyloid PET would exclude many participants from the final analysis, even though they had clinical/cognitive data. To maximize the data available for the clinical/cognitive analysis, an additional mITT population will be defined using CDR Global as the endpoint. 2. Change the external dataset used for the final analysis from DF17 to DF16 in section 5.4.1. Rationale for this change: Due to the early termination of the OLE study, the final analysis, including the data collected after

Author: ■■■

Version Number:

7

Version Date:

07Dec2023

Template No.: CS_TP_BS016 Revision 6

Reference: CS_WI_BS005

Effective Date: 02Dec2019

Unique Identifier for this Version	Date of the Document Version	Author	Significant Changes from Previous Authorized Version

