5.4.1. EXTERNAL CONTROLS

External control subjects will be identified by [REDACTED] and approved by Washington University from the associated DIAN-OBS data freeze (DF16 for both the interim analysis and the final analysis) based on matched DIAN-TU inclusion/exclusion criteria used to select external controls as described in Section 7.2 of the double-blind SAP (including the use of Appendix II and Section 12.1.2 in that SAP to calculate EYO), with the exceptions of CDR Global being used rather than components of the DIAN-MCE and some variable selections in [Table A](#) below

[REDACTED] [REDACTED]

Author: [REDACTED]	Version Number:	7
	Version Date:	07Dec2023

Template No.: CS_TP_BS016 Revision 6 Reference: CS_WI_BS005
 Effective Date: 02Dec2019

differing from those used in the double-blind SAP. The exception to the convention is that subjects already selected for double-blind period as Eligible DIAN-OBS subjects will be retained with the same baseline visit as identified in the double-blind selection.

[REDACTED] [REDACTED]

Author: [REDACTED]

Version Number: 7

Version Date: 07Dec2023

Template No.: CS_TP_BS016 Revision 6

Reference: CS_WI_BS005

Effective Date: 02Dec2019

Table A: DIAN-TU-001 Exclusion Criteria Specified in Protocol Amendment 10 That Can Be Validated Using Information from the DIAN-OBS Database

DIAN-TU-001 Exclusion Criteria	Corresponding DIAN-OBS Available Information	DIAN-OBS Data Source	Variable Names in DIAN-OBS (the values to remove)
4.2.3	Subjects with recent health history of stroke, cerebral hemorrhage or transient ischemic attack.	UDS Form A5 Subject Health History (Item 2a/2b)	CBSTROKE (1) CBTIA (1) Eligibility Baseline MCH (5+)
4.2.4	Subjects with alcohol or drug dependence sufficient to meet DSM-IV criteria currently or within the past 1 year.	UDS Form A5 Subject Health History (Item 7a,7c)	ALCOHOL (1) ABUSOTHR (1)
4.2.6, 7, 8, 9, 10	Subjects with recent myocardial ischemic events, congestive heart failure or major cardiovascular procedures including angioplasty / endarterectomy/stent, cardiac bypass procedure, pacemaker	UDS Form A5 Subject Health History (Item 1a,1c,1d,1e,1f)	CVANGIO (1) CVBYPASS (1) CVCHF (1) CVHATT (1) CVPACE (1)
4.2.3, 11	Subjects with active atrial fibrillation or in treatment with anticoagulation	UDS Form A4 Subject Medications UDS Form A5 Subject Health History (Item 1b)	DRUGID (d00210 d00022) CVAFIB (1)

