7.3. MISSING DATA

There will be no imputation of missing data. Handling of missing data for specific efficacy endpoints is detailed in [Sections 16.1.2](#) and [16.2.2](#).

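### SAP 16.2.4.1.1: the third amyloid group has no PiB criterion, so, read literally, participants and controls without a baseline PiB value are pooled with those whose amyloid stayed abnormal

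*SAP*

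**What the plan says.** The first paragraph of SAP 16.2.4.1.1 classifies everyone: "Each subject in the All Gant exposure mITT population and all controls will be categorized into 3 groups". The first two groups are "1) Amyloid normal group (both the baseline and the last available PiB SUVR values <1.25" and "2) Amyloid abnormal to normal group (the baseline PiB SUVR value ≥ 1.25 and the last available PiB SUVR value <1.25". The third is "3) The rest (not in groups (1) and (2". The hazard of CDR-SB progression is then compared across six cells, the three groups within baseline asymptomatic and symptomatic status.

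On who enters, SAP 5.3 states: "For analysis of clinical/cognitive endpoints or non-PET biomarker endpoints, the mITT population identified based on CDR Global should be used". The SAP's version 7 revision history explains why that population was extended to the final analysis: "many participants were unable to travel to the study site for the PET scan, resulting in significant missing data, either at baseline or post-baseline". For external controls, SAP 5.4.1 describes selection with "CDR Global being used rather than components of the DIAN-MCE" and states no PiB requirement. On missing values, SAP 7.3 says "There will be no imputation of missing data".

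The same grouping is reused for:
- time to first CDR-SB progression (16.2.4.1.2);
- the annual-rate model (16.2.4.1.3);
- the exponential and logistic progression models (16.2.4.1.4 and 16.2.4.1.5);
- CDR Global (16.2.4.2);
- the amyloid-clinical association (16.4).

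**The concern.** The third group is the comparator for participants who normalised. It is informative only if its members are known not to have normalised. A purely residual definition lets in people whose amyloid status is unknown, and the population rule makes sure such people can be present.

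The missing scans need not be unrelated to outcome. Protocol 4.4.1 and 6.3.7 let participants who stop treatment continue with whatever assessments they can manage, and allow PET to be omitted at early termination within 6 months of the last scan. A declining participant can therefore supply CDR data without a current scan. The cause the SAP names, pandemic travel, may be unrelated to progression. Since the documents do not settle which dominates, a reader of the results could not correct for it.

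**Working it through.** The plan states no sample size, power or scan count for this grouping, so there is no figure to reproduce. The check applies the rule as written to each scan pattern, then sizes the effect under declared assumptions.

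**Step 1. The rule applied literally (threshold 1.25)**

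| Baseline PiB | Last post-baseline PiB | Group |
|---|---|---|
| <1.25 | <1.25 | 1 |
| ≥1.25 | <1.25 | 2 |
| <1.25 | ≥1.25 | 3 |
| ≥1.25 | ≥1.25 | 3 |
| none | <1.25 | 3 |
| none | ≥1.25 | 3 |
| none | none | 3 |
| <1.25 | none | 1 if the baseline scan counts as *last available*, otherwise 3 |
| ≥1.25 | none | 3 on either reading |

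Group 3 therefore mixes persistently abnormal, normal-to-abnormal and unmeasured people. Someone with no baseline value whose last scan is below threshold also lands there.

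**Step 2. Does another section remove them?** SAP 7.3 and 16.1.2 concern imputing values. SAP 16.2.2 covers missing questionnaire items and composite components. None assigns or excludes a participant without PiB. The SAP is explicit elsewhere: 16.1.4.4 carries PiB values forward, baseline included, and adds a version without carrying forward. The second paragraph of 16.2.4.1.1 classifies on the last post-baseline scan. The first paragraph does neither.

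**Step 3. Illustrative size.** Let m be the unscanned share of group 3 and r their hazard relative to scanned members of group 3. Averaging hazards as a rough approximation, for group 2 versus group 3:

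HR_observed = HR_true / [(1 − m) + m·r]

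With HR_true = 1.00:
- m = 0.1, r = 1.5: 1 / (0.9 + 0.15) = 0.95
- m = 0.5, r = 2: 1 / (0.5 + 1.0) = 0.67
- m = 0.1, r = 0.5: 1 / (0.9 + 0.05) = 1.05
- m = 0.5, r = 0.5: 1 / (0.5 + 0.25) = 1.33
- r = 1, any m: 1.00

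Alternatively, suppose a share q of the unscanned had truly normalised and progress at the group 2 rate, the others progressing like scanned group 3:

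HR_observed = HR_true / [(1 − m·q) + m·q·HR_true]

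- m = 0.5, q = 0.75, true 0.50: 0.50 / (0.625 + 0.1875) = 0.615
- m = 0.5, q = 0.75, true 0.70: 0.70 / (0.625 + 0.2625) = 0.789
- q = 0: no change

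The values of m, r and q are assumptions. Neither document gives any of them.

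**The case against.** **Comparing values presupposes values.** Classification works by comparing two SUVRs with 1.25, and the SAP does not impute, so a programmer might simply drop unscanned people. That is a sensible choice, but it is not written down. The instruction to classify each subject, together with a residual category, says otherwise.

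**Few may be affected.** SAP 6.2.2 takes the latest non-missing pre-OLE measurement as OLE baseline, so a missed OLE scan can fall back on a double-blind one. Under SAP 5.3, participants given gantenerumab in the double-blind period use that period's baseline and may have its later scans. This stands as a point about size: the share could be small. It is not zero, because the revision history reports missing baseline PET, and PiB availability in external controls is not given.

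**The residual label is neutral.** The SAP does not call group 3 not normalised, and it includes normal-to-abnormal participants by design. True, but as the comparator to the normalised group it is read that way.

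**The fix selects on follow-up.** Requiring a later scan favours those who stayed long enough to have one. This stands, but it is not new: group 2 already requires a later scan.

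A reader might infer that this contrast is the SAP's evidence that amyloid removal slows progression. It is one of several lines. The second paragraph of 16.2.4.1.1 compares normal with abnormal on the last post-baseline scan and models the number of normal scans, and 16.4 item 1 correlates PiB change with clinical change. A reader might also infer that sicker, unscanned people inflate the contrast. The only cause the SAP names is travel during the pandemic, and analysis by symptomatic status and adjustment for baseline EYO take up part of any severity difference.

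**Conclusion.** The point holds as a defect in a classification rule. Read literally, group 3 contains participants and controls with no baseline PiB value or no PiB at all, and placement of someone with only a baseline scan below 1.25 depends on an undefined phrase. The contrasts of normalised participants with the remainder in 16.2.4.1.1 to 16.2.4.1.5, in 16.2.4.2 and in the mixed model of 16.4 item 2 can be biased. Neither the direction nor the amount can be derived from the documents; the figures under working show only what assumed inputs would do.

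The reach is limited. The primary PiB analysis (16.1.3) and the primary CDR analyses (16.2.3.1 and 16.2.3.2) do not use this grouping. The Table B interim models cite the second and third paragraphs of 16.2.4.1.1, or the third of 16.2.4.2, not this one. The correlations in 16.4 item 1 need a PiB change, so participants without a scan pair cannot enter them; the third group there would then be different people from those in the hazard models.

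**What to change.** In the first paragraph of SAP 16.2.4.1.1:
- Require a baseline PiB value and at least one post-baseline value for all three groups, and replace *last available* with last post-baseline.
- Define group 3 as a last post-baseline SUVR of 1.25 or more.
- Report participants and controls without a scan pair as not classifiable, with counts by treatment group and control source, outside the group contrasts.
- Apply the same definition in 16.2.4.1.2 to 16.2.4.1.5, 16.2.4.2 and 16.4.

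The cost is SAP wording and fewer participants in these supplemental contrasts. Those removed carry no usable information on whether amyloid normalised. Classification would still depend on staying in follow-up long enough to be scanned, as it does under the current rule, and the report should say so.
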